7.5.2. Duration of Response

DOR is defined as the time from the date of the first documented response (CR or PR) that is subsequently confirmed, to the earliest date of disease progression, as determined by IRR and investigator per RECIST v1.1, or death due to any cause. If a participant with a CR or PR has neither progressed nor died at the time of the analysis cutoff or at the start of any new anticancer therapy, the participant will be censored at the date of last adequate tumor assessment. The same rules used for censoring of PFS will be applied, see [Section 7.5.5](#) for more details. DOR will be calculated for participants who have achieved a confirmed response (i.e., CR or PR).

An estimate of the DOR survival function will be constructed using the KM method (Kaplan & Meier, 1958³) as implemented in PROC LIFETEST. The 25%, median, and 75% DOR (in months) will be summarized along with 95% confidence intervals as calculated from the PROC LIFETEST output (using method of [Brookmeyer & Crowley, 1982¹]).

Frequency distribution (<3 months, ≥3 months, ≥6 months, ≥9 months, ≥12 months, ≥24 months) will be provided.

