4.5. End of Study Definition

The end of study will occur 2 years after treatment initiation of the last enrolled patient or the point at which all patients have died or withdrawn consent or have been lost to follow up, whichever occurs first. At the end of the study, access to study treatment will be provided in accordance with applicable regulations and requirements to all patients who have not met the protocol-defined criteria for treatment withdrawal (see Section 6.7).

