8.4.2.1. Duration of Response

DOR, based on IRR and investigator assessments is defined as the time from the date of the first documented response (CR or PR) that is subsequently confirmed (by IRR and by

Version 5

Investigator, respectively) to the earliest date of disease progression, as determined by Investigator review of radiographic disease assessments and IRR per RECIST v1.1, or death due to any cause. If a patient with a CR or PR has neither progressed nor died at the time of the analysis cutoff or at the start of any new anticancer therapy, the patient will be censored at the date of last adequate tumor assessment. DOR will be calculated for patients who have achieved a confirmed overall response (i.e., CR or PR).

The survival distribution function for DOR will be estimated using the Kaplan-Meier method. In addition, descriptive statistics and frequency distribution will be provided.

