For reporting conventions, minimum and maximum values will be presented with the same decimal precision as collected in the raw data; mean, median, and quartiles should generally be presented to one more decimal place than the raw data; standard deviation should be displayed to two more decimal places than the raw data. Percentages will be reported to one decimal place. Unless otherwise noted, for all percentages, the number of participants in the analysis set who have an observation will be the denominator.

Data listings will be sorted by participant identifier, parameter, and the corresponding date of assessment. The listing source will be included in the footer of the listings.

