7.5. Efficacy Analysis

SS will be the primary population for the analysis of all efficacy endpoints. Depending on the recruitment rate for previously treated participants, a primary analysis may be performed separately for the treatment-naïve participant population. In any case, data will be summarized for treatment-naïve participants, previously treated participants, and overall.

The final analysis for ORR (Primary Completion Date) for treatment-naïve participants will take place after 14 months from the enrollment of the last treatment-naïve participant.

All efficacy endpoints, except OS, will be evaluated by IRR and by derived investigator-assessment in participants with *BRAF*^{V600E} mutant NSCLC, as determined by local test. Endpoints for derived investigator (hereafter referred to as investigator) will be derived programmatically from the target lesion measurements, non-target lesion status, and new lesions recorded on the eCRF, see details in [Section 10 \(Appendix 1\)](#).

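### The landmark summary of duration of response is a raw count only, so its ≥12 and ≥24 month shares run low when follow-up from response is short; no Kaplan-Meier rate at a fixed time is listed

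*SAP*

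**What the plan says.** **Censoring.** For a responder who has neither progressed nor died at the cutoff or at the start of new anticancer therapy, SAP 7.5.2 states: "the participant will be censored at the date of last adequate tumor assessment". DOR is computed for confirmed responders only.

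**Kaplan-Meier output.** "An estimate of the DOR survival function will be constructed using the KM method". The listed output is quartiles: "The 25%, median, and 75% DOR (in months) will be summarized along with 95% confidence intervals". Neither SAP 7.5.2 nor Protocol 8.4.2.1 lists a Kaplan-Meier probability at a fixed time.

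**Landmarks.** The SAP adds: "Frequency distribution (<3 months, ≥3 months, ≥6 months, ≥9 months, ≥12 months, ≥24 months) will be provided". The protocol's counterpart is equally brief: "In addition, descriptive statistics and frequency distribution will be provided". Neither says how censored durations enter the table.

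**Denominator.** SAP 7.1.9 gives the general rule, unless otherwise noted: "for all percentages, the number of participants in the analysis set who have an observation will be the denominator".

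**Timing.** SAP 7.5 says that the final ORR analysis for treatment-naïve participants "will take place after 14 months from the enrollment of the last treatment-naïve participant". No such rule is given for previously treated participants, yet SAP 7.1 puts both cohorts and the total in every table. Protocol 4.5 closes the study: "The end of study will occur 2 years after treatment initiation of the last enrolled patient", or earlier if no patient remains in follow-up.

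**The concern.** DOR is right-censored. A responder censored at 8 months has an observed DOR, so the default rule keeps that person in the denominator. The same person cannot be counted at ≥9, ≥12 or ≥24 months. The <3 and ≥3 month rows together cover all responders, so someone censored at 2 months sits beside those who progressed by then. A low share at a late landmark can then mean lost responses, short follow-up, or both, and the table as described does not let a reader tell which.

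Protocol 4.2 justifies a single-arm design by pointing to earlier approvals founded on response rates that were durable as well as meaningful. Readers will look to the 12 and 24 month landmarks for durability, and those are the rows most exposed. The two cohorts may also appear side by side with different follow-up.

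**Working it through.** The plan states no numerical target for DOR, so there is no planned figure to reproduce.

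**Inputs from the documents.** Scans every 8 weeks for 12 months, then every 12 weeks, each ±7 days (Protocol 7.2.3), read here as weeks 8 to 48, then 60, 72 and so on. One month = 30.4375 days, and durations count both end days (SAP 7.1.9). Treatment-naïve analysis 14 months after last enrollment (SAP 7.5). Reference median DOR in treatment-naïve patients 10.4 months, from the earlier dabrafenib plus trametinib study (Protocol 2.1.2). Expected responders 0.65 × 60 = 39 (SAP 4.3).

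**Assumptions not in the documents.** Exponential DOR; response at week 8; uniform accrual over 12, 24 or 30 months; first dose at enrollment; scans on nominal dates.

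**Step 1: follow-up from response.** Week 8 = 56/30.4375 = 1.84 months.
- Last treatment-naïve participant at the 14-month analysis: 14 − 1.84 = 12.16 months at most.
- Last patient enrolled in the study, at end of study: 24 − 1.84 = 22.16 months at most. This patient can never count at ≥24 months.
- The last scan before month 14 is week 60, so censored DOR is 52 weeks = 364 days = 11.96 months, or 365 days = 11.99 months with both end days counted. Either is just under 12 months (365.25 days).

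**Step 2: size by hand.** With censoring independent of DOR, raw share = P(DOR ≥ x) × P(observable to x).
- *≥24 months.* P(DOR ≥ 24) = 0.5^(24/10.4) = 0.202. With accrual A, P(follow-up from response ≥ 24) = (12.16 + A − 24)/A: 0.16/12 = 1.3%, 12.16/24 = 50.7%, 18.16/30 = 60.5%. Raw shares are therefore about 0.3%, 10.2% and 12.2%, against 20.2%.
- *≥12 months.* Everyone has at least 12.16 months from response, so the loss comes from the scan grid. Participants between month 14 and week 72 (month 16.56) at the cutoff have week 60 as their last scan: 2.56/A = 21.3%, 10.7%, 8.5%. Of these, 0.5^(11.96/10.4) = 45.1% are still responding and are missed. Loss: 9.6, 4.8 and 3.8 points.

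**Step 3: simulation.** 39 responders, 1,500 trials per scenario, with the scan grid and SAP censoring rule applied and administrative censoring only. Each range covers accrual over 12 to 30 months.

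| Landmark | Raw share, 14-month analysis | Kaplan-Meier, 14-month analysis | Raw share, end of study | Kaplan-Meier, end of study |
|---|---|---|---|---|
| ≥6 months | 69% | 69% | 69% | 69% |
| ≥9 months | 61% | 61% | 61% | 61% |
| ≥12 months | 34–40% | 44–45% | 45% | 45% |
| ≥24 months | 0–12% | 18–20% | 15–19% | 21–22% |

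For accrual over 12, 24 and 30 months, the gaps at the 14-month analysis are:
- ≥12 months: 43.8 − 34.2 = 9.6, 44.5 − 39.1 = 5.4, and 44.6 − 40.1 = 4.5 points.
- ≥24 months: 17.6 − 0 = 17.6, 19.9 − 9.1 = 10.8, and 20.3 − 11.5 = 8.8 points.

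These agree with the hand calculation.

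**Step 4: sensitivity.** With median DOR 18 months, the gaps at the 14-month analysis are 7 to 14 points (≥12 months) and 18 to 35 points (≥24 months). With a further 1% per month of other censoring and median 10.4 months, ≥6 months is 64% raw against 69% Kaplan-Meier.

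**The case against.** The best defense is that nothing planned is wrong. The Kaplan-Meier function and its quartiles handle censoring, the frequency line is an additional description, and a count of recorded durations of at least 12 months is a true statement about what was observed. Table layouts sit in a separate shell document (SAP 2), which may display censoring. Protocol 4.2 mentions durability when describing earlier approvals and then makes ORR the primary endpoint. Every hypothesis and decision rule concerns ORR, and no between-cohort comparison of DOR is planned.

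Most of this stands, and it rules out several stronger readings:

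- *That the SAP counts censored responders as having lost response.* It does not say so. It is silent, and the effect follows from the default denominator.
- *That durability as a whole is understated.* The median and the other quartiles are not affected by this table.
- *That every landmark is biased.* With at least 14 months of follow-up, ≥6 and ≥9 months are unaffected by administrative censoring for week-8 responders. A gap there needs other censoring, such as new therapy or loss to follow-up.
- *That the last-enrolled week-60 case proves bias at 12 months.* It misses by 0.25 day (365 against 365.25). Within the ±7-day window, a scan one day later gives 366 days = 12.02 months, which counts.
- *That a size can be given for previously treated participants.* No analysis date is set for them, so any figure would rest on invented follow-up.

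The defense does not supply an unbiased 12 or 24 month figure. The described table cannot give one while responders are censored before those times, and no other listed output does.

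**Conclusion.** The point holds as a minor one. SAP 7.5.2 gives landmark DOR only as raw frequencies and, under the default denominator, the late landmarks are too low. At the 14-month treatment-naïve analysis the understatement is about 5 to 10 points at ≥12 months and 9 to 18 points at ≥24 months, on the assumptions listed (exponential DOR, median 10.4 months, response at week 8, accrual over 12 to 30 months).

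The ≥24 month result is the firmer of the two: it follows from follow-up time, and a gap of about 3 to 6 points persists at end of study. The ≥12 month result depends on nominal scan dates around week 60, so variation within the scan window would move some participants across the line. It disappears by end of study if censoring is administrative only. For previously treated participants the direction is the same wherever follow-up is shorter than the landmark, but the size is unknown.

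No primary result, test or decision rule changes.

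**What to change.** Add one sentence to SAP 7.5.2: report Kaplan-Meier probabilities of ongoing response at 6, 9, 12 and 24 months with 95% CI and number at risk, by IRR and by investigator, in each cohort. If the frequency table is kept, label it as observed durations and show the number censored before each landmark.

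The number at risk matters most at 24 months. With 12-month accrual, the longest follow-up from a week-8 response at the 14-month analysis is 14 + 12 − 1.84 = 24.16 months, so the estimate would rest on almost nobody and should be shown as such. Kaplan-Meier rates remove the effect of administrative censoring. They do not settle whether censoring at new anticancer therapy is informative.

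The cost is that sentence and a few table rows. The estimates come from the PROC LIFETEST run already planned, and no data collection, sample size or protocol change is needed.

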7.5.3. Time to Response

Time to Response (TTR) based on IRR and investigator assessments is defined, for participants with a confirmed objective response, as the time, in months, from the date of first dose to the first documentation of objective response (CR or PR) which is subsequently confirmed. Time to response will be calculated for the subgroup of participants with a confirmed objective tumor response.

TTR will be summarized using descriptive statistics. In addition, the number and percent of participants with TTR in the following time intervals may be provided: 0 to <2 months, 2 to <4 months, 4 to <6 months, and ≥ 6 months.

7.5.4. Disease Control Rate

DCR is defined as the proportion of participants who have achieved a confirmed CR, confirmed PR or SD, as determined by IRR and investigator per RECIST v1.1 after 24 weeks (≥ 168 days) from the date of first dose of study drug.

DCR will be calculated along with the exact two-sided Clopper-Pearson 95% CI.

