| • To evaluate the efficacy of encorafenib + binimetinib in treatment-naïve and previously treated patients with BRAF ^{V600E} -mutant NSCLC as measured by DOR, DCR, PFS, and TTR | Confirmed ORR by Investigator per RECIST v1.1 DOR (by IRR and by Investigator) defined as the time from the date of the first documented response (CR or PR) that is subsequently confirmed (by IRR and by Investigator, respectively) to the earliest date of disease progression, per RECIST v1.1, or death due to any cause DCR (by IRR and by Investigator), defined as the proportion of patients who have a confirmed CR or confirmed PR, or SD per RECIST v1.1 PFS (by IRR and by Investigator), defined as the time from the date of first dose of study drug to the earliest date of disease progression, per RECIST v1.1, or death due to any cause TTR (by IRR and Investigator), defined as the time from the date of first dose to the first documentation of objective response (CR or PR) which is subsequently confirmed (by IRR and by Investigator, respectively) |
| • To evaluate the efficacy of encorafenib + binimetinib in treatment-naïve and previously treated patients with BRAF ^{V600E} -mutant NSCLC with respect to OS | • OS defined as the time from the date of first dose of study drug to the date of death due to any cause |
| • To evaluate the safety and tolerability of encorafenib + binimetinib in treatment-naïve and previously treated patients with BRAF ^{V600E} -mutant NSCLC | • Incidence and severity of AEs graded according to the NCI CTCAE v4.03 and changes in clinical laboratory parameters, vital signs, ECGs and ECHO/MUGA scans |

Overall Design:

Table 2 presents the study design elements.

| Study Phase | 2 |
|----------------------------|---|
| Type of Design | Open-label, multicenter, non-randomized study |
| Primary Purpose | Treatment: combination treatment with encorafenib + binimetinib in patients with $BRAF^{V600E}$ NSCLC |
| Intervention Model | Single Group |
| Clinical Indication | $BRAF^{V600}$ mutant NSCLC |

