3. OBJECTIVES AND ENDPOINTS

Table 5.Objectives and Endpoints

| Primary Objective | Primary Endpoint | |
|---|--|--|
| • To evaluate the efficacy of encorafenib + binimetinib in treatment-naïve and previously treated patients with BRAF ^{V600E} -mutant NSCLC as measured by ORR | • ORR defined as the proportion of patients who have achieved a confirmed best overall response (CR or PR) as determined by IRR per RECIST v1.1 in the treatment-naïve setting | |
| | • ORR defined as the proportion of patients who have achieved a confirmed best overall response (CR or PR) as determined by IRR per RECIST v1.1 in the previously treated setting. | |
| Secondary Objectives | Secondary Endpoints | |
| • To evaluate the efficacy of encorafenib + binimetinib in treatment-naïve and previously treated patients with BRAF ^{V600E} -mutant NSCLC as measured by DOR, DCR, PFS, and TTR | Confirmed ORR by Investigator per RECIST v1.1 DOR (by IRR and by Investigator) defined as the time from the date of the first documented response (CR or PR) that is subsequently confirmed (by IRR and by Investigator, respectively) to the earliest date of disease progression, per RECIST v1.1, or death due to any cause DCR (by IRR and by Investigator), defined as the proportion of patients who have a confirmed CR or confirmed PR, or SD per RECIST v1.1 PFS (by IRR and by Investigator), defined as the time from the date of first dose of study drug to the earliest date of disease progression, per RECIST v1.1 PTR (by IRR and Investigator), defined as the time from the date of first dose to the first documentation of objective response (CR or PR) which is subsequently confirmed (by IRR and by Investigator), defined as the time from the date of first dose to the first documentation of objective response (CR or PR) which is subsequently confirmed (by IRR and by Investigator) | |
| • To evaluate the efficacy of encorafenib + binimetinib in treatment-naïve and previously treated patients with BRAF ^{V600E} -mutant NSCLC with respect to OS | • OS defined as the time from the date of first dose of study drug to the date of death due to any cause | |
| • To evaluate the safety and tolerability of encorafenib + binimetinib in treatment-naïve and previously treated patients with BRAF ^{V600E} -mutant NSCLC | • Incidence and severity of AEs graded according to the NCI CTCAE v4.03 and changes in clinical laboratory parameters, vital signs, ECGs and ECHO/MUGA scans | |

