8. STATISTICAL CONSIDERATIONS

A detailed SAP will be prepared by the Sponsor or designee. This plan may modify the statistical methods outlined in the protocol; however, any major modifications of the primary endpoint definition or analysis will also be described in a protocol amendment.

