8.4.2.2. Disease Control Rate

Disease control rate is defined as the proportion of patients who have achieved a confirmed overall response of CR, PR or SD, as determined by Investigator review of radiographic disease assessments and IRR per RECIST v1.1. Additional information regarding DCR will be specified in the SAP.

DCR will be calculated along with exact two-sided 95% CIs.

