3. STUDY OBJECTIVES, ENDPOINTS AND ESTIMANDS

3.1. Study Objective and Endpoints

Table 2. Objectives and Endpoints

Primary Objective	Primary Endpoint

 To evaluate the efficacy of encorafenib + binimetinib in treatment-naïve and previously treated participants with BRAF^{V600E}-mutant NSCLC as measured by ORR 	
 ORR defined as the proportion of participants who have achieved a confirmed best overall response (CR or PR) as determined by IRR per RECIST v1.1 in the treatment-naïve setting ORR defined as the proportion of participants who have achieved a confirmed best overall response (CR or PR) as determined by IRR per RECIST v1.1 in the previously treated setting
Secondary Objectives	Secondary Endpoints

 To evaluate the efficacy of encorafenib + binimetinib in treatment-naïve and previously treated participants with BRAF^{V600E}-mutant NSCLC as measured by DOR, DCR, PFS, and TTR 	
 Confirmed ORR by investigator per RECIST v1.1 DOR (by IRR and investigator) defined as the time from the date of the first documented response (CR or PR) that is subsequently confirmed to the earliest date of disease progression, per RECIST v1.1, or death due to any cause DCR (by IRR and by investigator) defined as the proportion of participants who have achieved a confirmed CR, confirmed PR or SD per RECIST v1.1

Table 2. Objectives and Endpoints

	
 • PFS (by IRR and by investigator) defined as the time from the date of first dose of study drug to the earliest date of disease progression, per RECIST v1.1, or death due to any cause • TTR (by IRR and by investigator), defined as the time from the date of first dose to the first documentation of objective response (CR or PR) which is subsequently confirmed (by IRR and by Investigator)

 • To evaluate the efficacy of encorafenib + binimetinib in treatment-naïve and previously treated participants with BRAF^{V600E}-mutant NSCLC with respect to OS 	
 • OS defined as the time from the date of first dose of study drug to the date of death due to any cause

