10.4.1. Best Overall Response Evaluation for Each Participant

BOR is derived from the sequence of objective responses reported during the “Period for Derivation of Best Overall Response” according to the rules specified in the Oncology Rulebook.

Table 12 presents derivation of BOR for specific cases assuming that confirmation of response is required and is adapted from Eisenhauer EA, Therasse P, Bogaerts J, et al. New response evaluation criteria in solid tumours: Revised RECIST guideline (version 1.1). *Eur J Cancer*. 2009;45(2):228-47.

Table 12. Best Overall Response When Confirmation of Response is Required

Overall response first time point	Overall response subsequent time point	Best overall response
CR	CR	CR
CR	PR	SD, PD, or PR ^a
CR	SD	SD provided minimum criteria for SD duration met, otherwise PD
CR	PD	SD provided minimum criteria for SD duration met, otherwise PD
CR	NE	SD provided minimum criteria for SD duration met, otherwise NE
PR	CR	PR
PR	PR	PR
PR	SD	SD
PR	PD	SD provided minimum criteria for SD duration met, otherwise PD
PR	NE	SD provided minimum criteria for SD duration met, otherwise NE
NE	NE	NE

Note that best overall response of CR or PR requires confirmation ≥ 4 weeks after response is first observed. Minimum duration criteria for SD must be met for a best overall response of SD.

Abbreviations: CR = complete response; PR = partial response; SD = stable disease; PD = progressive disease; NE = not evaluable.

a. If a CR is *truly* met at first time point, then any disease seen at a subsequent time point, even disease meeting PR criteria relative to baseline, makes the disease PD at that point (since disease must have reappeared after CR). Best response would depend on whether minimum duration for SD was met. However, sometimes “CR” may be claimed when subsequent scans suggest small lesions were likely still present and in fact the participant had PR, not CR at the first time point. Under these circumstances, the original CR should be changed to PR and the best response is PR.

**Table 13. Best Overall Response When Confirmation of Response is Required:
Further Examples**

presents derivation of BOR for specific examples of overall response at sequential time points.

**Table 13. Best Overall Response When Confirmation of Response is Required:
Further Examples**

Overall response sequential time points	Best overall response

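### SAP 7.5.4 attaches a 24-week condition to DCR without limiting it to stable disease, and SAP Table 2 defines the same endpoint with no time condition

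*SAP*

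**What the plan says.** SAP 7.5.4 counts participants who have achieved "a confirmed CR, confirmed PR or SD, as determined by IRR and investigator per RECIST v1.1 after 24 weeks", and gives the time point as "after 24 weeks (≥ 168 days) from the date of first dose of study drug". One time phrase follows the whole list of response categories, and nothing ties it to SD alone.

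SAP Section 3.1, Table 2, defines the same endpoint as "the proportion of participants who have achieved a confirmed CR, confirmed PR or SD per RECIST v1.1", with no time condition. Protocol Table 5 agrees: "the proportion of patients who have a confirmed CR or confirmed PR, or SD per RECIST v1.1". Protocol Table 1 says the same, and Protocol 8.4.2.2 sets no time point either.

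The protocol does leave room for the SAP. Section 8.4.2.2 states "Additional information regarding DCR will be specified in the SAP", and Section 8 says of the SAP "This plan may modify the statistical methods outlined in the protocol".

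The SAP's best-response rules treat the categories differently. SAP 7.5.1 requires SD at 6 weeks or later, and the note to Table 12 in SAP 10.4.1 reads "Minimum duration criteria for SD must be met for a best overall response of SD". For CR and PR both places ask only for confirmation at least 4 weeks later.

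Protocol 7.2.3 schedules scans every 56 days with a 7-day window either side during the first 12 months.

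**The concern.** DCR is a named secondary endpoint, reported by IRR and by investigator, each with an exact 95% interval. Two programmers working from Table 2 and from 7.5.4 would produce different rates, and the SAP does not say which text prevails.

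Scope is the larger question. Followed literally, 7.5.4 can classify a participant as a confirmed responder for ORR and as not controlled for DCR, so DCR could be lower than ORR. For a rate that lists CR and PR among its components, that is hard to interpret.

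The day limit is a smaller matter. It falls exactly on the nominal day of the third scan, so status can turn on whether a compliant scan was taken a few days early.

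**Working it through.** **1. The stated limit.** 24 × 7 = 168 days = 3 × 56, the nominal third scan. The SAP's arithmetic is right.

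**2. Scan window.** The third scan may fall on days 161 to 175 after first dose, which is 15 allowed days. Days 161 to 167 miss a limit of 168: 7 of 15. If days are counted with the +1 used for durations in SAP 7.1.9, 6 of 15 miss it; 7.5.4 does not state the count. A participant who misses the limit can still qualify at the fourth scan (days 217 to 231). The 6-week SD minimum has no such problem: 42 days lies below the earliest compliant first scan, day 49.

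**3. Inputs for size (illustrative).**
- Exponential event times are assumed, with 1 month = 30.4375 days and P(event in d days) = 1 − exp(−ln 2 / median × d / 30.4375).
- Medians are the reference regimen's, from Protocol 2.1.2. DOR is 10.4 months (CI 8.3, 17.9) in treatment-naïve and 9.0 (6.9, 18.3) in previously treated patients. PFS is 10.9 (7.0, 16.6) and 10.2 (6.9, 16.7).
- Responders at the design rates: 65% of 60 = 39, and 45% of 37 = 16.65.
- SD as best response is assumed at 20% (range 10 to 30%). The documents give no figure.

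**4. Literal reading: responders lost by week 24.** Every response is taken as first seen at week 8. It is then confirmed at week 16 (next scheduled scan, 56 days at risk) or at week 12 (4-week minimum, 84 days at risk).
- Naïve: 0.115 × 39 = 4.5; 0.168 × 39 = 6.6. Over the CI of the median: 2.7 to 8.0.
- Previously treated: 0.132 × 16.65 = 2.2; 0.191 × 16.65 = 3.2. Over the CI: 1.1 to 4.0.

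**5. When DCR would fall below ORR (literal reading).** Divide the responders lost by the chance that an SD participant, event-free at week 8, is still event-free at week 24 (0.791 naïve, 0.779 previously treated).
- Naïve: 4.5/0.791 = 5.7 and 6.6/0.791 = 8.3 of 60, or 9.5% and 13.8%.
- Previously treated: 2.2/0.779 = 2.8 and 3.2/0.779 = 4.1 of 37, or 7.6% and 11.1%.

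DCR drops below ORR only if the SD rate is under these figures.

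**6. SD-only reading: participants moved by the 24-week rule.** P(event by week 24, given event-free at week 8) is 0.209 naïve and 0.221 previously treated.
- 0.209 × 60 × 0.20 = 2.5. Range 0.9 (10% SD, upper CI limit of median) to 5.5 (30% SD, lower limit).
- 0.221 × 37 × 0.20 = 1.6. Range 0.5 to 3.4.

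**7. Window effect.** Those affected are event-free at day 168, have an event before day 224, and had an early third scan. Scan days are assumed to be spread evenly over the window. S(d) is the probability of being event-free at day d.
- SD only: [S(168) − S(224)]/S(56) = 0.087 and 0.092. Then 0.087 × 60 × 0.20 × 7/15 = 0.49 (0.42 with 6/15), and 0.092 × 37 × 0.20 × 7/15 = 0.32 (0.27 with 6/15). At 30% SD and the lower CI limit of median PFS: 0.97 and 0.60.
- Literal reading: S(168) − S(224) = 0.078 and 0.081. Times 7/15 or 6/15 and the group size, this gives 1.9 to 2.2 of 60 and 1.2 to 1.4 of 37.

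**The case against.** The protocol hands DCR detail to the SAP, and endpoint tables are summaries that leave out much operational detail. A reader might infer that the SAP departed from the protocol by adding 24 weeks, or that omitting it from SAP Section 6 is a defect. The documents support neither: adding detail is the route the protocol lays down, and a Section 6 entry is optional.

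Two other readings of 7.5.4 are coherent. The 24 weeks may be a minimum duration for SD, which the best-response rules favour. Or it may define a landmark rate at week 24, in which case a responder who has already progressed is meant to be excluded and a DCR below ORR is no error. A reader might infer that the plan certainly drops confirmed responders; that follows only from the literal reading.

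The responder losses are also generous. A response first seen at week 16 cannot be confirmed before week 20, so it has little time at risk before week 24. The SD rate is assumed, and the PFS medians describe all treated patients, not those with SD. The scan window matters little if only SD is governed, and any later qualifying scan rescues the participant.

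What stands is that the SAP does not say which reading applies, and that its two definitions give different rates.

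**Conclusion.** The point holds as a minor one. The SAP carries two unreconciled definitions of a secondary endpoint, and the one in the methods section, as worded, is at odds with best-response rules that place a minimum duration on SD alone.

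Under the literal reading the effect is a handful of responders per group, and the figures in step 4 lie towards the high end because they assume every response is first seen at week 8. Under an SD-only reading the 24-week rule moves roughly two or three of 60 and one or two of 37 at 20% SD, and the missing window affects fewer than one per group. All sizes rest on exponential times, the reference regimen's medians and, where used, an assumed SD rate and evenly spread scan days.

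DCR has a confidence interval but no hypothesis test. Nothing here touches the primary ORR analysis, its alpha or its power.

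**What to change.** Use one DCR definition in SAP 7.5.4 and Table 2. Count any confirmed CR or PR as disease control, and apply the 24-week duration to SD only. Set the limit to allow the 7 days by which a scan may be early, that is, at least 161 days after first dose (Study Day 162 under SAP 7.1.3), and state the day count.

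If a 24-week landmark rate is what is intended, name it as such and report it separately from DCR.

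An entry in SAP Section 6 would help readers but is not required. The cost is a few lines of SAP text; no new data are needed.
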